#### 4.9.1.3 Handling of Dropouts or Missing Data

Any patients that are discharged from the hospital prior to Day 14 due to improvement of clinical status and their status on Day 14 cannot be obtained, then the Last Observation Carried Forward (LOCF) approach will be used to impute missing data. Only post-treatment observations will be carried forward. No baseline observations will be carried forward. To assess the robustness of the study conclusions to the choice of imputation method, a complete-case analysis (all patients with missing data for the primary endpoint are excluded from analysis) will be performed as a sensitivity analysis.

The Per-protocol population analyses will be performed using the same imputation method as for the ITT population analyses.

If the proportion and/or pattern of missing data is found to be different to that assumed, additional sensitivity analyses may be required.

In general, imputed partial dates will not be used to derive study day, duration (e.g., duration of adverse events), or elapsed time variables. In addition, imputed dates are not used for deriving the last contact date in the time to event analyses.

Imputed dates will not be displayed in listings unless otherwise stated.

The partial date imputation will follow ADaM conventions. The ADaM approach is to populate the numeric date variables with the imputed date and add a flag variable to the dataset that indicates the level of imputation.

The flag variable can contain the values: blank, 'D', 'M', 'Y'.

blank: indicates that no imputation was done

- D='Day': indicates that the day portion of the date is imputed
- M='Month': indicates that the month and day portions of the date are imputed
- Y='Year': indicates that the entire date (year, month, and day) is imputed

Imputing partial AE and prior/concomitant medication start dates:

- a) If the year is unknown, the date will not be imputed and will be assigned a missing value.
- b) If the month is unknown, then:

1. If the year matches the first dose date, then impute to the month and day of the first dose date.
2. Otherwise, assign 'January'.

c) If the day is unknown, then:

1. If the month and year match the first dose date, then impute to the day of the first dose date.
2. Otherwise, assign '01'.

Imputing partial AE and prior/concomitant medication stop dates:

- a) If the year is unknown, the date will not be imputed and will be assigned a missing value.
- b) If the month is unknown, then assign 'December'.
- c) If the day is unknown, then impute to the last day of the month.

Imputing partial death dates:

- a) If the month and/or year are unknown, the death date will not be imputed.
- b) If the day is missing, then assign '01'.
- c) If imputing the first day of the month results in a negative overall survival time, the patient will be censored for overall survival at the randomization date.

A patient data listing will be provided showing all patients with missing values for the primary endpoint. For these patients, the listing will provide all observed data relating to the primary endpoint (i.e. all measurements recorded prior to the missing value, any measurements recorded after the missing value, important baseline characteristics, the recorded reason for study discontinuation, and the date of study discontinuation). The listing will also provide the imputed date(s) used in the primary analysis.

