#### 4.7 Prior, Concomitant Medication and Prohibited Medication

Prior and concomitant medications will be summarized by drug class and preferred medication name by treatment group and for both treatment groups combined (Total) using the ITT population. Prior and concomitant medications will be summarized separately, concomitant medications will also be summarized overall and by study period. WHO DDE March 2020 will be used to classify medications.

Medication start and stop dates will be compared to the date of first dose of study drug to allow medications to be classified as either Prior only, both Prior and Concomitant, or Concomitant only. Missing or partial start dates will be imputed as described in [Section 4.9.1.3](#). Medications starting after the completion/withdrawal date will be listed but will not be classified or summarized.

Medications that start and stop prior to the date of first dose of study drug will be classified as Prior only. If a medication starts before the date of first dose of study drug and stops on or after the date of first dose of study drug, then the medication will be classified as both Prior and Concomitant. Medications will be classified as Concomitant only if they have a start date on or after the date of first dose of study drug.

Rescue medication of a ready-to-use nebulization of a bronchodilator will be allowed on study. The number and percentages of the patients using such medications will be summarized by treatment groups, and the impact on efficacy and safety will be analyzed by subgroup analyses.

By-patient listings of prior, concomitant and rescue medications will be provided. Listings will also be provided for any concomitant procedures reported.

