A by-patient listing of all AEs will be provided. This listing will be presented by treatment arm and will include: center, patient identifier, age, gender, race, adverse event (SOC, PT, and verbatim term), date of onset, date of resolution, duration, severity, seriousness, action taken, outcome, and relatedness. The following AE listings will also be provided using a similar layout:

- Patients who died during the study
- Patients with treatment-emergent SAEs
- Patients with treatment withdrawal due to AEs
- Patients with dose reduction due to AEs
- Patients with dose interruption due to AEs

For missing or partially missing dates, imputation will be done according to [Section 4.9.1.3](#).

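### Partial start dates are set to the first dose date without checking the stop date, so a medication that ended before dosing is tabulated as concomitant

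*SAP*

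**What the plan says.** SAP section 4.9.1.3 has a block headed "Imputing partial AE and prior/concomitant medication start dates". Two of its rules matter here.

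- Month unknown, rule (b)1: "If the year matches the first dose date, then impute to the month and day of the first dose date". Otherwise January is assigned.
- Day unknown, rule (c)1: "If the month and year match the first dose date, then impute to the day of the first dose date". Otherwise the first of the month is assigned.

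The stop-date rules in the same section move a partial stop as late as possible: "If the day is unknown, then impute to the last day of the month", and December if the month is missing. A complete stop date stays as recorded. No rule compares the imputed start with the stop.

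Section 4.7 uses the imputed dates for classification: "Missing or partial start dates will be imputed as described in" section 4.9.1.3. It then states "Medications that start and stop prior to the date of first dose of study drug will be classified as Prior only" and "Medications will be classified as Concomitant only if they have a start date on or after the date of first dose of study drug". The second of these tests the start date alone.

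Section 4.10.1 applies the same imputation to adverse events: "For missing or partially missing dates, imputation will be done according to" section 4.9.1.3.

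**The concern.** Placing an uncertain start at first dose is a common and defensible convention when the record leaves open whether the start came before or after dosing. A recorded stop before first dose removes that uncertainty, because the start must also lie before first dose. Rules (b)1 and (c)1 override this known fact. The result is a start later than its own stop, and a medication that belongs in the prior table appears in the concomitant table.

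Section 4.7 summarizes prior and concomitant medications separately, and concomitant medications also by study period. In an open-label trial these tables help a reader judge what treatment patients had before entry and what they received on study. The error moves pre-study treatment into the on-study column. Section 4.9.1.3 also keeps imputed dates out of listings unless otherwise stated. A listing would therefore show a stop before dosing for a drug that the table counts as concomitant, with nothing to explain the disagreement.

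**Working it through.** The plan gives no figure to reproduce, so the check applies the rules as written.

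**Inputs.** Start-date rules (b)1 and (c)1 and the stop-date rules come from section 4.9.1.3; the three classes come from section 4.7. The first dose date of 15 October 2020 is assumed for illustration.

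**Rules in short form**, with F the first dose date, S the imputed start and E the stop:

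- Day missing, month and year equal to those of F: S = F.
- Month missing, year equal to that of F: S = F.
- S < F and E < F: Prior only.
- S < F and E ≥ F: Prior and Concomitant.
- S ≥ F: Concomitant only.

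**Single records.**

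| Recorded start | Stop | Imputed start | Class under 4.7 |
|---|---|---|---|
| Oct 2020, day missing | 8 Oct 2020 | 15 Oct 2020 | Concomitant only; start 7 days after stop |
| 2020, month missing | 30 Jun 2020 | 15 Oct 2020 | Concomitant only; start after stop |
| Sep 2020, day missing | 8 Oct 2020 | 1 Sep 2020 | Prior only (correct) |
| Oct 2020, day missing | 20 Oct 2020 | 15 Oct 2020 | Concomitant only (acceptable; true start uncertain) |

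**All cases for this first dose date.**

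- Day missing: a stop on day b of October, with b from 1 to 14, has b possible true start days from the 1st. The number of pairs is 1 + 2 + … + 14 = 14 × 15 / 2 = 105. All 105 give S = 15 October, later than E, and Concomitant only.
- Month missing: the stop can be any day from 1 January to 14 October 2020. That is 274 days to the end of September plus 14, or 288. All 288 give the same wrong result.

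The counts depend on the assumed date. The logic does not: whenever E < F and the rule sets S = F, S is later than E and the class is wrong.

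**Where the fault stops.** A start in a known earlier month gets day 01, and a start in an earlier year gets January, so neither is affected. A stop that lacks its day in the month of first dose moves to month end, on or after F, and no inversion arises. A stop that lacks its day in an earlier month of the same year moves to the end of that month, still before F. Combined with a start known only by year, it does invert.

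**Is it corrected elsewhere?** Section 4.9.1.3 bars imputed dates from study day, duration, elapsed time and last contact date. Classification as prior or concomitant is not on that list. The same section does check imputed death dates for a negative survival time, but has no similar check here.

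**After the change.** With the start set to 1 October (day missing) or 1 January 2020 (month missing), S ≤ E < F in every one of the 105 and 288 cases, so all become Prior only. Records with a stop on or after F keep their class.

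**The case against.** The strongest reply is that the fault is narrow and has little consequence. It needs a partial start matching the month or year of first dose together with a stop known to precede dosing. The bar on using imputed dates for durations prevents negative durations. By-patient medication listings are provided. Medication class enters neither the primary analysis nor the models for the secondary endpoints, and baseline comparability is also shown by the characteristics, strata and medical history in section 4.6. All of this stands and keeps the point minor. It does not make the classification right.

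A reader might infer more than the text supports in three ways.

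- **That pre-dose events enter the treatment-emergent table.** Affected adverse events do get a start after their stop. However, section 4.10.1 uses the term treatment-emergent without an onset rule, so the effect holds only if it means onset on or after first dose. Section 3.1 limits screening to at most 2 days before treatment. If events are collected from consent (an assumption), an affected event would have to start and end within that window and still lack its start day.
- **That drugs still ongoing at first dose are wrongly denied Prior status.** With only the year, or month and year, recorded, such a drug may have started before or after dosing. Placing it at first dose is a convention under real uncertainty, not an error.
- **That a percentage of medication records can be named.** The SAP gives no share of partial dates, and even that share would overstate the affected subset.

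**Conclusion.** The point holds for medications, and it is minor. As written, sections 4.9.1.3 and 4.7 together misclassify every medication whose partial start matches the first dose year, or month and year, and whose stop is known to precede first dose. The full rate within that set follows from the rules and needs no assumption about dates. The size of the set cannot be stated from the SAP.

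For adverse events, the inverted dates follow from the text. Any effect on the treatment-emergent counts is conditional on an onset-based definition and is likely very small.

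Only descriptive medication tables, and possibly adverse event tables, are affected. No primary, key secondary or mortality result changes.

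**What to change.** Add to rules (b)1 and (c)1 of section 4.9.1.3: unless the known or imputed stop date is before the first dose date, in which case impute the first day of the known month (or January 1 of the known year).

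The words *or imputed* cover the record with a year-only start and a stop lacking its day in an earlier month. Section 4.7 needs no change, because the corrected start leads to the right class.

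The cost is one clause in the SAP and a small change to the derivation of imputed start dates. No new data are needed.

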#### 4.9.1.4 Multiple Comparisons/Multiplicity

To account for the multiple testing due to the second interim analysis an adjustment for the type-I-error probability will be applied using the Haybittle-Peto approach with one sided alpha=0.0005 at the second interim analysis and leave one-sided nominal alpha of 0.0249 for the final analysis.

#### 4.9.1.5 Interim Analyses

Two interim analyses will be performed.

1. The first analysis will be conducted when about 60 participants (40 participants in the RESP301+SOC arm and 20 participants in the SOC arm) have completed the Day 10 assessment. The purpose of this analysis is to evaluate efficacy of RESP301 with the application of a futility criterion based on the results on SpO2 change from baseline on Day 10. The following futility criterion will be used for this first interim analysis:

If the difference in the percentage of participants with at least a 2% improvement in SpO2 between both treatment arms is less than 5%, benefit of RESP301 treatment is not expected. For a final decision to stop the study for futility the results on other endpoints associated with safety and efficacy will be considered as well.

As no other modification of the study at the time of the first interim analysis is considered, no adjustment of the alpha level is required.

2. The second interim analysis will be conducted after 150 participants (100 participants in the RESP301+SOC arm and 50 participants in the SOC arm) have completed the Day 14 assessment. The purpose of this analysis is the assessment of futility or a sample size re-estimation (increase only) in case the actual results differ from the original assumptions for the power calculations of the study, related to the percentage of participants meeting the primary endpoint in the control arm and/or the relative treatment benefit achieved in the RESP301+SOC arm compared to the SOC arm.

To account for the multiple testing due to the second interim analysis an adjustment for the type I error alpha will be applied using the Haybittle-Peto approach which would spend one sided alpha=0.0005 at the second interim analysis and leave one-sided nominal alpha of 0.0249 for the final analysis. The futility criterion for the second interim analysis will be based on the conditional power (CP) for the final results based on the assumption that the remainder of the study will follow the same trend as observed in the interim analysis. If CP at the time of the second interim analysis is less than 20% consideration will be given to stop the study for futility. At the same time sample size re-estimation will be performed to achieve 80% power at the end of the study.

#### 4.9.1.6 Examination of Subgroups

The treatment effect for the primary and key secondary efficacy endpoints will be examined for the following subgroups:

1. Country
2. Age >65 years
3. Ongoing or currently treated diabetes mellitus
4. Ongoing or currently treated hypertension
5. Ongoing or currently treated cardiovascular disease
6. Ongoing or currently treated chronic lung disease
7. Cancer history of less than 3 years, basal cell skin carcinoma excluded

## 8. Ongoing or currently treated chronic kidney disease

Summaries of the primary and key secondary efficacy variables by treatment group and subgroups will be produced. No formal statistical analysis will be performed within subgroup.

With reviewing the results, the homogeneity of the treatment effect across subgroups may be investigated using graphical and analytical methods.

### 4.9.2 Primary Efficacy Variable

Progression to level at least one level higher than baseline of modified WHO ordinal COVID-19 scale by Day 14”

The WHO 7-point ordinal scale is as follows:

1. Not hospitalized, no limitations on activities;
2. Not hospitalized, limitation on activities;
3. Hospitalized, not requiring supplemental oxygen;
4. Hospitalized, requiring supplemental oxygen;
5. Hospitalized, on non-invasive ventilation or high-flow oxygen devices;
6. Hospitalized, on invasive mechanical ventilation or ECMO;
7. Death.

The percentage and corresponding 95% CI of patients who progress to at least one level higher from baseline on the WHO 7-point ordinal scale on Day 14 will be summarized by treatment arm and overall. The odds ratio of RESP301 + SOC versus SOC alone and 95% CI intervals and p-values will be estimated using the CMH stratified by country and number of risk factors (as randomized).

WHO 7-point ordinal scale will be assessed daily while patient is hospitalized. Daily scores and changes from baseline will be summarized. Plots of mean score (with standard error bars) by treatment group over time may be produced.

A by-patient listing of the primary efficacy data will be provided

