### 3.3 Endpoints

#### 3.3.1 Efficacy Variables

Primary:

- Proportion of participants who progress to level >4 of modified WHO ordinal scale due to COVID-19 by Day 14

Key Secondary:

- Change in room air SpO2 from baseline over time
- Change in NEWS 2 symptom score from baseline over time
- Change from baseline on the modified WHO ordinal scale at each visit up to Day 28
- Time to improvement to at least one level lower of the modified WHO ordinal scale
- Time to progression to at least one level higher of the modified WHO ordinal scale

Additional Secondary:

- Time to hospital discharge
- Incidence of mortality by Day 28

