All the categorical variables including the primary endpoint will be summarized by treatment in terms of the number of patients providing data at the relevant time point (n), frequency counts and percentages. Binary primary endpoint: (progression to critical stage/death up to Day 14) will be analyzed by a Cochran-Mantel-Haenszel (CMH) stratified for the factors used in the stratified randomization. Treatment difference will be tested using a Cochran–Mantel–Haenszel (CMH) test stratified by 1) country and 2) participant's clinical status at Baseline. For the categorical endpoints, relative risk and its 95% CI will be presented.

Percentages will be presented to one decimal place. Percentages will not be presented for zero counts. Percentages will be calculated using n as the denominator. If sample sizes are small, the data displays will show the percentages, but any textual report will describe frequencies only.

Changes from baseline in categorical data will be summarized using shift tables where appropriate.

P-values greater than or equal to 0.001, in general, will be presented to three decimal places. P-values less than 0.001 will be presented as “<0.001”.

Confidence intervals will be presented to one more decimal place than the raw data.

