## 4.9 Efficacy Evaluation

### 4.9.1 Analysis and Data Conventions

This study is designed to test for superiority. The null hypothesis for the treatment comparison will be that there is no difference in the rate of progression to at least one level higher of the modified WHO ordinal scale in RESP301 + SOC compared to SOC alone. The alternative hypothesis is that RESP301 +SOC reduces the rate of progression to at least one level higher in the modified WHO ordinal scale in COVID-19 at Day 14. Symbolically, this is expressed as follows:

$$\begin{aligned} H_0: p\text{WHO+1+RESP301+SOC} &\geq p\text{WHO+1+SOC} \\ H_a: p\text{WHO+1+RESP301+SOC} &< p\text{WHO+1+SOC} \end{aligned}$$

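### The SAP defines the primary event both as progression at any time up to Day 14 and as status on Day 14, and its LOCF rule does not protect a recorded progression

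*SAP*

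**What the plan says.** All references are to the current SAP, version 2.0.

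Cumulative wording:
- Section 3.3.1, primary endpoint: "Proportion of participants who progress to level >4 of modified WHO ordinal scale due to COVID-19 by Day 14".
- Section 4.9.2, opening line: "Progression to level at least one level higher than baseline of modified WHO ordinal COVID-19 scale by Day 14".
- Section 4.2, on the binary primary endpoint: "progression to critical stage/death up to Day 14) will be analyzed by a Cochran-Mantel-Haenszel (CMH".

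Day 14 status wording:
- Section 4.9.2, the sentence that specifies the summary: patients who "progress to at least one level higher from baseline on the WHO 7-point ordinal scale on Day 14".
- Section 4.9.1, alternative hypothesis: "rate of progression to at least one level higher in the modified WHO ordinal scale in COVID-19 at Day 14".
- Section 4.9.1.3, imputation. The rule covers patients "discharged from the hospital prior to Day 14 due to improvement of clinical status and their status on Day 14 cannot be obtained" and fills the gap by LOCF, using post-treatment values only. The complete-case sensitivity analysis is one in which "all patients with missing data for the primary endpoint are excluded from analysis".

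Section 4.9.2 also has the ordinal scale recorded every day in hospital. Time to progression in Section 4.9.3 runs to the date of an increase. No section says that an earlier worsening counts as an event whatever the patient's level on Day 14.

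**The concern.** Take a patient at level 4 who goes to level 5 or 6, recovers and is discharged on Day 12. Under the cumulative wording this is an event. Under the Day 14 wording it is not. The primary objective in Section 2.1 is to prevent progression. Status on Day 14 answers a different question, namely whether a worsening persists.

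The missing-data rules make this more than a loose preposition. With a cumulative event, a patient whose progression was recorded in hospital has a known outcome and nothing to impute. Section 4.9.1.3 makes no such exception: what triggers imputation is a missing Day 14 status, not a missing event outcome. The last value before an improved discharge will usually be at or below baseline, so carrying it forward erases the progression.

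The second interim analysis uses the primary event rate (Section 3.1), so the choice of reading also affects futility and sample size re-estimation. The trial is open-label, and two available event definitions leave room to choose between them with outcomes in view.

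**Working it through.** **Step 1. Trace hypothetical patients, all at level 4 at baseline.**

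| Course | Cumulative reading | Day 14 status reading |
|---|---|---|
| Goes to level 5, back at level 4 in hospital on Day 14 | Event | Not an event |
| Goes to level 6, discharged improved on Day 12, reached by telephone on Day 14 | Event | Not an event |
| Same, but Day 14 status not obtained | Event, nothing to impute | LOCF carries the last score: not an event. Excluded from complete-case |
| Dies before Day 14 | Event | Event (level 7 persists) |

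The readings differ only for patients who worsened and recovered. Deaths are unaffected. The LOCF and complete-case consequences in the third row arise only on the status reading.

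**Step 2. Reproduce the plan's own figure.** The sample size sections are redacted, so Appendix A is the only table that can be checked. Inputs: 50 SOC and 100 RESP301+SOC patients at the second interim, 300 planned, and one-sided 0.0249 at the final analysis (Section 4.9.1.5), for which the critical value is 1.9617. The unpooled variance is my choice, because it fits the table.

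- z1 = (pS − pR) / √[pS(1 − pS)/50 + pR(1 − pR)/100]
- CP = 1 − Φ[(1.9617 − w1·z1)/w2 − z1·√(n2/n1)], with w1 = w2 = √(150/300) = 0.7071 and n1 = n2 = 150
- This reduces to CP = 1 − Φ(2.774 − 2·z1)

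For 15/50 v 15/100: z1 = 0.15/√(0.0042 + 0.001275) = 0.15/0.0740 = 2.027, and CP = 1 − Φ(−1.280) = 90%. Appendix A states 90%. Over the whole table, 17 of 18 conditional power values agree within 2 points. The exception (12/50 v 20/100) is not used here.

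**Step 3. Change only the number who recover.** Assume 15/50 v 15/100 ever progressed. Appendix A does not say which reading its counts represent, and the SAP gives no recovery share, so the shares below are assumptions.

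| Recovered by Day 14 (SOC, RESP301) | Counted on Day 14 | z1 | CP computed | Appendix A: CP | Appendix A: total N for 80% |
|---|---|---|---|---|---|
| 0, 0 | 15/50 v 15/100 | 2.027 | 90% | 90% | no increase |
| 3, 3 | 12/50 v 12/100 | 1.750 | 77% | 77% | 321 |
| 5, 5 | 10/50 v 10/100 | 1.562 | 64% | 64% | 412 |
| 3, 0 | 12/50 v 15/100 | 1.283 | 42% | 42% | above the 600 cap |
| 5, 0 | 10/50 v 15/100 | 0.747 | 10% | 10% | above the 600 cap |
| 0, 5 | 15/50 v 10/100 | 2.801 | 99.8% | 99% | no increase |

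The same patients can therefore give no action, a re-estimation, or a value below the 20% at which Section 4.9.1.5 has stopping considered. Appendix A does not itself label the 10% row an early stop.

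**The case against.** A reader might infer that the SAP has settled on Day 14 status, so that recovered patients will be scored as successes. The document does not support that. Three statements are plainly cumulative, and Section 4.2 attaches its wording to the endpoint being tested. The sentences with *on* and *at* still speak of progressing or of a rate of progression, and could mean the rate reached by that day. What stands is a contradiction, not an established scoring rule.

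The LOCF point is also narrow. It covers patients discharged improved whose status cannot be obtained, and Section 3.1 provides a Day 14 telephone contact, so the group should be small. Nothing says that LOCF overwrites a recorded progression, and the complete-case exclusion of progressors follows only if the status reading is already assumed. Against this, nothing prevents either outcome. The listing rule in Section 4.9.1.3, which asks for measurements before and after the missing value, treats the endpoint as a value at one time point.

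A second tempting inference is a definite loss of power. The documents do not support that either. The design event rates are redacted, and Appendix A's rates are illustrations. The direction depends on how recovery divides between the arms. At a fixed 300 with assumed rates of 30% v 15% (pooled null variance), power is 84.9%. It becomes 74.5% if 20% of progressors recover in both arms, 30.1% if 40% of SOC and 20% of RESP301 progressors recover, and 92.1% if those two shares are swapped. These figures also ignore the re-estimation, which would recover part of any loss.

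Escalations are not lost altogether, since time to progression and the daily summaries keep them. The protocol and the SAP Addendum cited in Section 4.12 were not seen and may fix the derivation. None of this removes the need for the SAP to state one rule for its primary event.

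**Conclusion.** The point holds as an internal contradiction in the primary endpoint. Sections 3.3.1, 4.2 and the first line of 4.9.2 are cumulative. The analysis sentence of 4.9.2, the hypothesis in 4.9.1 and the LOCF rule in 4.9.1.3 work on Day 14 status. Followed literally, the second group turns a worsening with recovery into a non-event, can let LOCF replace a recorded progression, and drops such patients from the complete-case analysis.

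The size cannot be fixed from the SAP, because it depends on how many progressors recover by Day 14 and in which arm. The Appendix A illustration gives conditional power of 77% or 64% instead of 90% with equal recovery of 3 or 5 of 15 per arm, and 10% to 99% with unequal recovery of 5 patients. That is enough to change the interim decision, so the rule should be settled before the primary analysis is run.

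**What to change.** Use one rule in Sections 3.3.1, 4.2, 4.9.1, 4.9.1.3 and 4.9.2:

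- The event is any recorded qualifying progression, including death, at any time up to Day 14.
- LOCF applies only to patients with no recorded progression and cannot overwrite one.
- A recorded progression counts as an event in every analysis, including complete-case.
- Status on Day 14 is reported as a separate summary.

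The same edit must say what qualifies. Section 3.3.1 requires a level >4 due to COVID-19, while Sections 4.9.1 and 4.9.2 require at least one level above baseline. A patient who goes from level 3 to level 4 is an event only under the latter. A missing-equals-progression or tipping-point analysis is a separate choice and not part of this fix.

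The cost is wording in five sections and a small change to the derivation. No new data are needed: the in-hospital scores are already daily, and time to progression already uses the date of increase.
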